5.7 OTHER ANALYSES

5.7.1 Summaries of Conduct of Study

In Study Period A, the number of participants who enroll, discontinue from treatment, discontinue from study, and complete the study will be tabulated by treatment group. Reasons for early discontinuation of treatment or early termination from the study will be listed and summarized by treatment group. Any eligibility criteria and other major protocol deviations will also be summarized by treatment group. The summaries of conduct of study will be based on the ITT population; randomized non-carriers will also be grouped and presented in this section.

5.7.2 Summaries of Treatment Group Comparability/Demographics and Baseline Characteristics

Demographic and baseline characteristics such as age, sex, race, APOE4 status, and baseline cognitive scores will be summarized for the ITT population by treatment group using descriptive statistics; randomized non-carriers will also be grouped and presented in this section. Baseline is defined as the last-available measurement obtained on or prior to randomization.

5.7.3 Summaries COVID-19 Impact on the Trial

The study was ongoing during the COVID-19 pandemic. Consequently, to monitor the potential impact of the pandemic on the trial, we will provide a specific set of descriptive analyses related to COVID-19, including:

- COVID-19 adverse event
- COVID-19-related protocol deviations
- Missed doses due to COVID-19
- Study discontinuations due to COVID-19
- Remote scale administrations
- Site actions and site closures

5.7.4 Pharmacokinetic and Pharmacodynamic Analyses

Mean serum and CSF crenezumab concentration versus time data will be tabulated and plotted, as appropriate. In serum, trough plasma concentration ($C_{trough, ss}$) will be tabulated and summarized (e.g., mean, standard deviation, minimum, and maximum). Additional PK analyses, such as evaluating relationships between crenezumab concentrations, PD biomarkers, efficacy and safety endpoints, may be conducted as appropriate. Mean plasma total $A\beta_{1-40}$ and $A\beta_{1-42}$ concentrations versus time will be tabulated and plotted, as appropriate. The relationship between crenezumab and total $A\beta_{1-40}$ and $A\beta_{1-42}$ concentrations will be tabulated and plotted to explore the peripheral PK/PD relationship, *as appropriate*.

The schedule for PK and PD analyses will be independent of the safety and efficacy endpoints.

5.8 ANALYSES IN TAU PET LONGITUDINAL SUBSTUDY BN40199

In this section, we outline the main statistical details in the tau PET longitudinal Substudy BN40199. The analysis populations in this substudy are described in detail in Section 4.

The primary endpoint of the tau PET longitudinal substudy is the annualized rate of change in the tau PET SUVr in the entorhinal cortex (Braak Stage 1), and other ROIs, including whole cortical gray matter, may be explored based on evidence in presymptomatic ADAD populations. The analysis population is based on mITT among the mutation carriers. The primary analysis in the tau PET longitudinal substudy will be performed using an RCRM. This model will include the actual tau PET SUVr as the response variable. The model set up is similar to the RCRM in the primary analysis model in the main study.

The 95% CI and p-value for crenezumab treatment effect will be presented. The estimated crenezumab treatment effect compared with the placebo group on the RR scale will also be presented. *Similar to secondary imaging endpoints (Sections 5.4.1 and 5.4.2)*, at the initial study readout, the Sponsor will analyze at least the *first* and last-available (in time) tau PET data. If the result from the main Study GN28352 is positive (at least one of the primary endpoints is statistically significant), the Sponsor will further analyze all available tau PET data and the p-value will be instead based on the full data.

The MMRM analysis may also be used to explore the treatment benefit over time. Additional descriptive summaries that describe the relationship between tau PET SUVr and biomarker and clinical endpoints are specified in Section 1.1.

Summaries of conduct of the substudy and summaries of demographic and baseline characteristics will be presented in a similar fashion to the main study; the analyses will be based on the ITT population; randomized non-carriers will also be grouped and presented in this section.

The main safety analyses planned for Study Period A (see Section 5.6) of the safety data collected during the tau substudy will also be performed in the tau substudy safety-evaluable population (see Section 4 for definition).

5.9 INTERIM ANALYSES

No interim analyses to be conducted.

5.10 ANALYSES FOR PERIOD B AND OPEN-LABEL EXTENSION STUDY

This section will pre-specify the main analyses planned for Study Period B of this study and the potential OLE study.

If the Sponsor decides to terminate the study based on the primary analysis results from Study Period A, all the data and analyses from Study Period B will be considered as exploratory in nature; a final CSR will be written, including these extra data. However, if the Sponsor decides to extend Study Period B or initiate an OLE study, a planned data snapshot will occur 2 years after finished the last efficacy visit in Study Period A.

Three analysis populations are defined for this snapshot:

- Study Period A mITT population: the mITT population defined in Section 4: all randomized participants who received at least 1 dose of study drug; participants are grouped according to the treatment assignment at randomization; all efficacy analyses in this snapshot are based on mITT population among the mutation carriers
- Study Period B safety population: all randomized participants that received at least 1 dose of study drug in Study Period B; participants are grouped according to the actual treatment received; participants on placebo who received more than 2 doses of crenezumab will be grouped in the crenezumab arm
- OLE safety population: all OLE enrolled participants that received at least 1 dose of study drug (crenezumab)

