The common-close design will increase the power of detecting a difference between crenezumab and placebo by utilizing the data obtained from each participant, including those data from participants with more than 5 years' treatment duration, in the overall analysis. Furthermore, the common-close design allows similar duration of treatment with the higher IV dose (60 mg/kg IV) or matching placebo, for analysis of treatment at a higher dose.

The rationale for changing the study design is to maintain statistical power of 80% to detect a treatment effect (see Section 4.10 for further details)—despite the fact that only 252 participants of the 300 originally planned could be recruited from this kindred—and to allow reasonable duration of treatment for assessment of benefit at the higher dose.

Study Period A will be continued until the last ongoing enrolled participant has reached 260 weeks, as far as is practical (see Section 4.5.4).

One or more interim analyses may be conducted at the Sponsor's discretion at any point during the study. Such an analysis may be triggered by, for example, the availability of results from another clinical study with crenezumab.

3.2.1

Rationale for Study Period B

For the first participants reaching the final efficacy visit in Study Period A (End of Treatment-A or End of Treatment-B visit), several months will pass before results from Study Period A are available *and a longer period of time until regulatory approval or a mechanism of post-trial access is set up*. To honor the long commitment of participants and not to force a treatment gap in the case crenezumab is effective in slowing disease progression, participants will be offered the opportunity to continue to receive blinded study drug until *regulatory approval or post-trial drug access is started* (via an OLE or other program) or there is a decision to terminate the development of crenezumab on the basis of the results in Study GN28352. *Data collected in Study Period B will be used to assess the long term safety and efficacy of crenezumab.* Continuation into Study Period B is optional.

Treatment and Dosing

After completing the final efficacy visit in Study Period A, all mutation carriers who enter Study Period B will receive crenezumab and all non-carriers entering Study Period B will continue to receive placebo. Participants, site staff, vendor staff, and Sponsor will

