3.6 STUDY PARTICIPANTS AND ANALYSIS GROUPS

The *Study Period A* primary efficacy analysis will be based on a modified intent-to-treat (mITT) population. This consists of participants who are mutation carriers treated with

any amount of study drug. Participants in the efficacy analysis population will be grouped based on treatment assigned.

Safety assessments will be performed for safety-evaluable participants, defined as all randomized participants who have received at least 1 dose of study drug. Because of the importance of assessing safety on the basis of actual drug received by a participant (especially with respect to cerebral VE, superficial siderosis of the CNS, and cerebral micro- or macrohemorrhages), participants will be grouped for all safety analyses according to the treatment they actually received rather than the treatment assigned at randomization and mutation-carrier status.

The Study Period B safety population is based on all randomized participants that received at least 1 dose of study drug in Study Period B. Participants will be grouped according to the actual treatment received.

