4.10.4 Safety Analysis

The safety analysis population in Study Period A will consist of all carrier participants with at least one dose of study medication. The participants in this population will be grouped according to treatment received.

If the Sponsor decides to initiate an OLE study, safety data from Study Period B will also be used to contribute to the safety analysis in the OLE study. In this case, the safety analysis population in Study Period B will be grouped according to the treatment received in Study Period B. Safety assessments will be on the basis of adverse event reports, the results of vital signs, physical examinations, MRI evaluations, immunogenicity as measured by ADAs, and clinical laboratory tests.

Observed toxicities and adverse events will be coded and tabulated using the MedDRA; the frequencies of participants who receive active medication and those who receive placebo will be compared using descriptive statistics and reviewed for potential clinical significance and importance. Treatment-emergent adverse event tabulations will be provided overall, by severity, for serious adverse events, and further subcategorized by relationship to study drug.

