1.2 STUDY DESIGN

1.2.1 Study Period A

This is a prospective, randomized, double-blind, placebo-controlled, parallel-group study of crenezumab versus placebo in individuals who carry the *PSEN1* E280A autosomal-dominant mutation causing early-onset Alzheimer's disease (EOAD), and do not meet criteria for mild cognitive impairment (MCI) due to Alzheimer's disease (AD) (Albert et al. 2011) or dementia due to AD (McKhann et al. 2011) and are, thus, in a preclinical phase of AD (Sperling et al. 2011). The study also incorporates administration of placebo to individuals who are not *PSEN1* E280A autosomal-dominant mutation carriers. This efficacy and safety study is being conducted at a single primary site and 3 satellite sites in Colombia.

In the Study GN28352, *PSEN1* E280A autosomal-dominant mutation carriers who met study eligibility criteria were randomized in a 1:1 ratio to one of two treatment groups: crenezumab or placebo. Crenezumab is being administered either SC (720 mg every 2 weeks) or IV (60 mg/kg every 4 weeks). Matching placebo is administered by the same routes at the same dosing regimen. The switch to the higher IV dose (approximately 4-fold higher exposure to crenezumab) was optional. Participants may decide whether to change from the SC dosing route to the IV dose route; however, once IV dosing in a given participant has occurred, it is not intended for a participant to switch back to the lower SC dose. In order to maintain genotype blind

and to have a genetic kindred control, a cohort of *PSEN1* E280A mutation non-carrier kindred family members were also enrolled in the study and dosed only with placebo.

The study includes three arms *and originally aimed to have approximately 100 participants per arm*; two arms with participants that have a *PSEN1* E280A mutation randomized in a 1:1 ratio to active treatment or placebo and a third arm of non-carriers randomized to placebo (see [Figure 1](#)). Participants will receive the randomized treatment until the last participants have reached their last treatment visits at 260 weeks (see [Figure 2](#)).

[figure not shown]

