1.2.2 Study Period B

Following the completion of Study Period A, participants will be offered the opportunity to continue to receive study drug until the results of the study are known. This is termed Study Period B. All *PSEN1* mutation carriers will be provided crenezumab in Study Period B regardless of treatment allocation during Study Period A, and all non-carriers will continue on placebo. Treatment allocation for both Study Periods A and B will remain blinded. Study Period B may last up to approximately 12 months depending on when participants enter Study Period B. See [Figure 2](#).

[figure not shown]
*After the primary efficacy results from Study Period A are available, the Sponsor may extend Study Period B, or initiate an OLE study for *PSEN1* E280A autosomal-dominant mutation carriers, or development of crenezumab may be discontinued.*

Figure 1 Study Design

RCT = randomized, controlled trial.

Figure 2 Study Schematic

ETA/ETB = end of treatment visit A or end of treatment visit B; OLE = open-label extension; SFU = safety follow-up; W = week.

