5.10.2 Safety Analyses

If the Sponsor decides *to terminate the study based on the primary analysis results from Study Period A*, then safety data from Study Period B will be reported in the final CSR. The Study Period B safety population is defined in the beginning of Section 5.10.

If the Sponsor decides *to extend Study Period B or initiate an OLE, then safety data from Study Period B will be reported in the final CSR and safety data from the OLE will be summarized in the OLE CSR*. The OLE safety population is defined in the beginning of Section 5.10.

All the safety analyses described in Section 5.6 will be reported.

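### Period B safety is grouped only by treatment received, so former placebo carriers starting crenezumab share one column with carriers treated with it for at least 260 weeks by design

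*SAP*

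**What the plan says.** SAP 5.10 defines the Period B safety population as randomised participants with at least one Period B dose, and states that "participants are grouped according to the actual treatment received; participants on placebo who received more than 2 doses of crenezumab" go into the crenezumab arm. Protocol 3.6 has the same population ("The Study Period B safety population is based on all randomized participants that received at least 1 dose of study drug in Study Period B") and the same rule: "Participants will be grouped according to the actual treatment received". Protocol 4.10.4 repeats it for the case in which an open-label extension is started: "the safety analysis population in Study Period B will be grouped according to the treatment received in Study Period B".

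On treatment, Protocol 3.2.1 says that "all mutation carriers who enter Study Period B will receive crenezumab", and SAP 1.2.2 confirms that "mutation carriers will be provided crenezumab in Study Period B regardless of treatment allocation during Study Period A". Non-carriers stay on placebo.

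On the tables, SAP 5.10.2 says "All the safety analyses described in Section 5.6 will be reported". Section 5.6 summarises by treatment group; only exposure is also broken down, by SC or IV route. Neither document splits Period B safety by Period A arm or by time since first crenezumab dose. The efficacy analyses of the same data snapshot do keep the arm assigned at randomisation.

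**The concern.** Grouping by treatment received usually keeps a safety table honest. In Period B it yields one crenezumab column holding essentially all carriers, and that column contains two different risk sets. Former placebo carriers are receiving the antibody for the first time. Carriers randomised to crenezumab have already had a long course, and those who stopped because of adverse events are under-represented among them. Injection and infusion reactions and hypersensitivity are the kinds of event most likely to differ between the two.

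A mixed column describes neither group well. It dilutes an initiation effect, and it also gives no clean rate for long-term treatment, although long-term safety is a stated Period B objective (Protocol 2.5). The placebo column cannot help, because non-carriers differ by genotype and were not randomised against carriers.

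**Working it through.** The documents give no figure for this point, so there is none to reproduce. The check is whether the grouping rule does pool the two sets, and by how much that dilutes.

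**Does it pool?** All carriers in Period B receive crenezumab, so treatment received is the same for both Period A arms. The rule about more than 2 doses does not undo this. It does not say whether the placebo assignment meant is that of Period A or Period B, but on either reading a former placebo carrier who continues past two doses is counted under crenezumab.

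**How much does it dilute?** Let w be the share of former placebo carriers among carriers dosed in Period B, p1 the event rate in new starters and p0 the rate in experienced carriers.

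- Pooled rate = w × p1 + (1 − w) × p0
- Excess shown over p0 = w × (p1 − p0)

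So the pooled column shows a fraction w of an excess confined to new starters.

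**Inputs for w.** Carriers "were randomized in a 1:1 ratio to one of two treatment groups: crenezumab or placebo" (SAP 1.2.1). The SAP Appendix 2 simulation, set up to resemble this study, uses 84 per arm with no dropout. SAP 3 assumes 25% dropout, and 84 × 0.75 = 63. Actual Period B entry is not given and is optional, so the splits below are assumptions. The last pair is a deliberately wide imbalance.

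| Former placebo : former crenezumab | w |
|---|---|
| 84 : 84, or 63 : 63 | 0.50 |
| 63 : 84 | 63/147 = 0.43 |
| 84 : 63 | 84/147 = 0.57 |
| 50 : 75 | 50/125 = 0.40 |
| 75 : 50 | 75/125 = 0.60 |

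**If experienced carriers keep part of the excess.** With a retained fraction f, the factor is w + (1 − w) × f. At w = 0.50 this is 0.625 for f = 0.25, 0.75 for f = 0.5, and 1.0 (no dilution) for f = 1.

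**Illustration with assumed rates** of 10% in new starters and 2% in experienced carriers:

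- Split columns: excess 10 − 2 = 8 points, ratio 10/2 = 5.
- Pooled, w = 0.50: rate 0.5 × 10 + 0.5 × 2 = 6%, excess 4 points, ratio 6/2 = 3.
- Pooled, w = 0.43 to 0.57: rate 5.4% to 6.6%, excess 3.4 to 4.6 points.

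**The case against.** The strongest reply is that first exposure has already been studied under better conditions. Period A compares crenezumab with concurrent randomised placebo carriers from the first dose, with MRI about every 3 months in the first year (Protocol 3.5.2.1). This stands. A reader might infer that the plan leaves first-exposure risk unassessed; it does not. The point concerns what the Period B tables add.

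A reader might also infer that a split would settle early ARIA and immunogenicity. The Period B schedules do not support that. Routine MRI is at Week 105 (or at early termination if sooner) plus symptom-driven scans, and routine ADA sampling is at Week 105 and the early termination or safety follow-up visit (Protocol 3.5.2.1, Appendices 5 and 6). Few cases are likely in any event: ADA was found in 2 of 397 exposed patients in one Phase III study at 60 mg/kg (Protocol 1.2.2.3), and 84 × 2/397 is about 0.4 expected.

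Nor is early versus delayed start a protected randomised safety contrast. Entry is optional and follows at least 260 weeks of selection. The early-start group is not uniformly long-exposed to its current dose either: IV dosing was offered only from July 2019, and carriers still on SC may switch on entering Period B (Protocol 3.2.1 and 3.2.2).

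Finally, the SAP introduction promises only general descriptions of Period B safety, these data become exploratory if the study is terminated, events of special interest are reported within 24 hours, and an internal committee monitors Period B safety (Protocol 5.1.3 and 3.5). So participant protection does not rest on these tables. They still go into the final study report, however, and the stated rule yields a pooled column only.

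**Conclusion.** The point holds as one of presentation. As written, the plan reports new starters and long-treated carriers together, with non-carriers as the only other column. An excess specific to first exposure would appear at about 50% of its size with equal entry from the two arms, and at about 40% to 60% over the imbalances tried. The stronger reading, that pooling halves any safety signal, is not supported: an effect that persists in experienced carriers is diluted less or not at all (a factor of 0.75 if they keep half of it).

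These figures rest on assumed entry numbers, and the event rates used are illustrative. The practical gain is mainly for reported adverse events and injection or infusion reactions.

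**What to change.** In SAP 5.10, and in Protocol 3.6 and 4.10.4 to match, present all Period B safety summaries in three columns:

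- carriers randomised to crenezumab (early start);
- carriers randomised to placebo (delayed start);
- non-carriers on placebo.

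A pooled crenezumab column can be kept as an addition. State that the early-versus-delayed comparison is descriptive among those who rolled over. Defining the carrier columns by Period A arm also removes any doubt about where a former placebo carrier with only one or two crenezumab doses is counted.

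The cost is a change of wording and one grouping variable, the Period A assignment, which is already held. No new data or visits are needed. SAP 5.10.1.2 already has the Sponsor unblinded when analysing Period A results, so tables by arm are feasible while participants and blinded site staff remain blinded to Period A allocation.

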5.10.1 Efficacy Analyses

All efficacy analyses will include data from Study Period A, Study Period B, and the OLE study; the analysis population will be based on mITT. *The delayed start efficacy analyses will be triggered 2 years after the last efficacy visit in Study Period A.*

Two types of efficacy analyses are prespecified depending on the endpoint type: delayed-start analyses for continuous endpoints and rank-preserving structural failure time (RPSFT) analyses for time-to-event endpoints.

5.10.1.1 Delayed-Start Analyses

The delayed-start analysis will be used for all continuous efficacy endpoints that will be collected in Study Period B and the potential OLE study. Since the potential OLE will not be published by the finalization of this SAP, the description in this section is in general terms and does not focus on any specific endpoint. However, statistical testing will be performed only on the API ADAD Composite Cognitive Test total score and the FCSRT Cueing Index. Other continuous efficacy endpoints, including clinical endpoints, fluid biomarkers, and imaging biomarkers, will be considered exploratory and thus, formal statistical testing will not be done.

Figure 4 illustrates the concept of the delayed-start analysis. As shown in the figure, a treatment effect is assumed in Period A of Study GN28352; the disease progression slope of mutation carriers from the Study Period A crenezumab arm is assumed to be the same in Study Period B and in the OLE; the disease progression slope of mutation carriers from the Study Period A placebo group; however, will have a different slope in Study Period B and in the OLE. The statistical model details can be found in

Appendix 3. To control the type I error within the delayed-start analyses, the fixed testing sequence is specified in the following figure. The α level in each testing is a two-sided 0.05. If at any stage the null hypothesis H_0 is not rejected, then the formal testing procedure will stop.

Figure 4 Illustration of Delayed-Start Analyses Using Data from the Beginning of Period A of Study GN28352 to the End of Study Period B or OLE

[figure not shown]
[figure not shown]

Figure 5 Testing Hierarchy for Delayed-Start Analyses

API = Alzheimer's Prevention Initiative; ADAD = autosomal-dominant Alzheimer's disease; FCSRT = Free and Cued Selective Reminding Task.

Note: For a definition of H0 and H1, please see Section 2.

